2.3.1.1 Pembrolizumab (Parts 3 and 4 only)

Among the many immunotherapeutic strategies, immune checkpoint blockade enhances a cancer patient's immune system to fight an array of cancers. By increasing the activity of the immune system, immune checkpoint blockade can induce inflammatory side effects known as immune-related Adverse Events (irAE). Although any organ system can be affected, irAEs most commonly involve the gastrointestinal tract, endocrine glands, skin, and liver. Less often, the CNS and cardiovascular, pulmonary, musculoskeletal, and hematologic systems are involved. The wide range of potential irAEs requires multidisciplinary, collaborative management by providers across the clinical spectrum.

Immune-related adverse reactions may be mild to moderate in severity but can be severe or fatal and can occur in any organ system or tissue in patients receiving pembrolizumab and may also occur after discontinuation of treatment. For suspected immune-mediated adverse reactions, there should be adequate evaluation to confirm etiology and exclude other causes.

The key safety risks for pembrolizumab include immune-related toxicities, infusion-related reactions, and embryofetal toxicity (Table 6). Refer to Section 6.2.2.2 for specific recommendations regarding the mitigation and management of these risks.

Refer to the pembrolizumab Investigator's Brochure for additional safety information.

Table 6 Potential Risks for Pembrolizumab

Safety Risk	Description
Immune-related toxicities	Immune-related adverse effects associated with PD-1 blocking agents include pneumonitis, colitis, hepatitis, endocrinopathies, nephritis and renal dysfunction, skin reactions, encephalitis, vasculitis, sclerosing cholangitis, and other immune-related adverse reactions.
Infusion-related reactions	Signs and symptoms may include pyrexia, chills, rigors, flushing, urticaria, hypotension, dyspnea, wheezing, headache, back pain, and abdominal pain.
Embryofetal toxicity	Blockade of PD-1 signaling has been shown in animal models of pregnancy to disrupt tolerance to the fetus and to result in an increase in fetal loss; therefore, there is the possibility of fetal harm if administered during pregnancy.

PD-1 = programmed cell death 1

2.3.1.2 NL-201 Combination With Pembrolizumab (Parts 3 and 4 only)

Based on biological mechanism of action and initial clinical safety information from the monotherapy study with NL-201, the key safety risks described for monotherapy would also be expected along with the potential risks described for pembrolizumab. Moreover, with combination treatment, AEs may be more severe and occur at different time points and/or dose levels in comparison to monotherapy. In particular, target-dependent and target-independent synergistic activation of T-cells is expected and may contribute to more severe immune-related toxicities.

Potential safety risks for the combination of NL-201 and pembrolizumab include:

- Exacerbated cytokine release syndrome and/or infusion-related reactions
- Exacerbation of autoimmune/inflammatory disorders
- Exacerbation of autoimmune AEs

Patients will be monitored closely in a hospital setting for 24 hours after receiving their first dose in the first cycle. The pre-medication requirements are expected to mitigate many of the NL-201 associated toxicity.

Dose and schedule of pembrolizumab administration will be according to the approved label 200 mg every 21 days. Patients will be monitored for 30 minutes following pembrolizumab administration before NL-201 infusion is initiated. The starting dose of NL-201 in combination with pembrolizumab will be one dose level below the highest cleared dose.

Refer to the individual Investigator's Brochures for a more detailed assessment.

2.3.2 Benefit Assessment

NL-201 has been shown to effectively stimulate T-cell and NK-cell mediated antitumor activity in multiple animal models of cancer, in some cases more effectively than check-point inhibitors or IL-2. The agent is engineered to have no binding affinity for CD25, which is hypothesized to improve its safety profile. Indeed, animal safety experiments have demonstrated tolerability of NL-201 in multiple species (see [Section 2.2.2](#)), and published reports show that the parent protein Neo-2/15 is less toxic than natural IL-2.⁵ An individual patient in the study may see benefit from NL-201 by experiencing stable disease (SD) or an objective response. They may potentially experience a durable CR, as has been observed with IL-2 therapy in advanced solid cancer patients. Clinical benefit in this open-label study will be estimated based on progression-free survival (PFS), ORR, and response duration. Parts 3 and 4: It is hypothesized that NL-201 in combination with pembrolizumab may improve response to pembrolizumab as was demonstrated in animal models. NL-201 has been shown to increase PD-1 expression in CD⁺ T-cells, increased the immune infiltration of the TME, and may make tumor cells more sensitive to the effects of pembrolizumab.

Refer to the individual Investigator's Brochures for a more detailed assessment.

2.3.3 Overall Benefit: Risk Conclusion

Patients will have advanced and incurable disease and will have exhausted all approved therapies. Under the controlled setting of clinical investigation, NL-201 offers a reasonable potential of clinical benefit. The patient will weigh the risk vs potential benefit based on informed consent.

3 OBJECTIVES AND ENDPOINTS

Parts 1 and 2 (NL-201 Monotherapy)

OBJECTIVES	ENDPOINTS
Primary	

 Assess the safety and toxicity profile of NL-201 in patients with advanced solid tumors Define the recommended phase 2 dose (RP2D) and schedule of NL-201 	
 Dose-limiting toxicities (DLTs) Incidence and severity of treatment-emergent adverse events and clinically significant changes in vital signs, electrocardiograms (ECGs), and clinical laboratory tests
Secondary	

 Characterize the pharmacokinetic (PK) profile of NL-201 	
 PK parameters including but not limited to area under the serum concentration time curve (AUC), maximum observed serum concentration (C_{max}), half-life ($t_{1/2}$), clearance (CL), and volume of distribution (Vd)

 Estimate the immunogenicity of NL-201 	
 Antidrug antibodies in serum during and after treatment with NL-201

 Estimate the antitumor activity of NL-201 per Response Evaluation Criteria in Solid Tumors (RECIST) 1.1 and RECIST for use in cancer immunotherapy trials (iRECIST) criteria 	
 Best objective response Objective response rate Duration of response Progression-free survival (PFS)
Exploratory	

 Investigate the pharmacodynamic biomarkers of NL-201 	
 Flow-cytometry analysis of immune cells in blood, eg, for markers of T-cell activation and exhaustion, eg, cluster of differentiation (CD)4, CD8, CD25, forkhead box P3 (FoxP3) Serum measurements of inflammatory cytokine levels Analysis of immune characteristics of the tumor microenvironment (eg, multiplex immunohistochemical, transcriptional profiling)

 Estimate additional measures of antitumor activity of NL-201 per RECIST 1.1 and/or iRECIST criteria 	
 Overall survival (OS) Clinical benefit rate

Parts 3 and 4 (NL-201 in Combination with Pembrolizumab)

OBJECTIVES	ENDPOINTS
Primary	

 Assess the safety and tolerability of NL-201 in combination with pembrolizumab in patients with advanced solid tumors Define the RP2D and schedule of NL-201 in combination with pembrolizumab 	
 DLTs Incidence and severity of treatment-emergent adverse events and clinically significant changes in vital signs, ECGs, and clinical laboratory tests
Secondary	

 Characterize the PK profile of NL-201 in combination with pembrolizumab 	
 NL-201 PK parameters including but not limited to AUC, C_{max}, $t_{1/2}$, CL, and Vd

OBJECTIVES	ENDPOINTS

 Estimate the immunogenicity of NL-201 in combination with pembrolizumab 	
 NL-201 antidrug antibodies in serum during and after treatment with NL-201 in combination with pembrolizumab

 Estimate the antitumor activity of NL-201 in combination with pembrolizumab per RECIST 1.1 and iRECIST criteria 	
 Best objective response Objective response rate Duration of response PFS
Exploratory	

 Investigate the pharmacodynamic biomarkers of NL-201 in combination with pembrolizumab 	
 Flow-cytometry analysis of immune cells in blood for modulation of lymphocyte subsets, including markers of T-cell activation and exhaustion, including CD4, CD8, CD25, FoxP3 Serum measurements of inflammatory cytokine levels Analysis of immune characteristics of the tumor microenvironment (eg, multiplex immunohistochemical, transcriptional profiling)

 Evaluation of exploratory biomarkers including pharmacodynamic and potential patient selection biomarkers 	
 PD-L1 expression in tumors (as available) Tumor microenvironment (TME) immune score (as available)

 Estimate additional measures of antitumor activity of NL-201 in combination with pembrolizumab per RECIST 1.1 and/or iRECIST criteria 	
 OS Clinical benefit rate

4 STUDY DESIGN

4.1 Overall Design

This is a Phase 1 first-in-human, open-label, dose escalation and cohort-expansion study of NL-201 that will be conducted in 4 parts.

Parts 1 and 2 (NL-201 Monotherapy)

Part 1 will be an adaptive modified toxicity probability interval (mTPI) design dose escalation study in adult patients with advanced solid tumors to determine safety profile and the recommended Phase 2 dose (RP2D) and treatment schedule of NL-201 as monotherapy. Part 1 will include IV (Schedule A and B), each with up to approximately 50 patients. In addition, there will be backfill cohorts (up to approximately 12 patients in total), at certain DMC-cleared dose levels and schedules, to collect, PK, PD and response data in certain tumor types or to explore additional pre-medication regimens (eg, steroids). The decision to enroll patients into backfill cohorts and to define the patients to be enrolled will be made by the Sponsor. Part 1 will enroll up to approximately 115 adult patients in total.

Part 2 will be a Simon 2-stage dose expansion cohort study in patients in 2 indications (up to n = 30 per cohort) with exploratory paired biopsies to estimate the tolerability and antitumor activity of NL-201 as monotherapy in these indications.

Parts 3 and 4 (NL-201 in Combination with Pembrolizumab)

Part 3 will be an adaptive mTPI design dose escalation study in up to 42 adult patients with advanced solid tumors to determine the safety profile, RP2D and treatment schedule of NL-201 in combination with pembrolizumab. Part 4 will be a dose expansion phase in 3 cohorts (up to n = 30 per cohort) to confirm the combination RP2D and obtain additional estimation of pharmacokinetics (PK), pharmacodynamics (PDn), and antitumor activity.

All Parts

Patients will enter the screening period, up to 28 days prior to Cycle 1 Day 1 of treatment. PK, PDn, and exploratory tumor biopsy samples will be obtained per the study Schedule of Events (see [Section 1.3](#)). Tumor response to treatment will be assessed by radiographic evaluation per Response Evaluation Criteria in Solid Tumors (RECIST) 1.1 and RECIST for use in cancer immunotherapy trials (iRECIST) every 6 weeks for 12 weeks, and every 12 weeks thereafter while on treatment. Patients may continue on treatment until unacceptable toxicity, disease progression per iRECIST with either confirmation or clinical decline, completion of 35 administrations (approximately 2 years) with pembrolizumab (for Parts 3 and 4), withdrawal of consent, patient or physician decision, study termination, or death. Patients with progressive disease who are considered to be clinically stable and whose progression is considered to be minimal are required to have a confirmatory scan and tumor evaluation after the initial determination of progression. Patients with progressive disease per RECIST criteria may continue on treatment past progression if, in the opinion of the Investigator, the patient is considered to be clinically stable or has experienced clinical benefit from NL-201 alone or in combination with pembrolizumab (see [Section 6.1.1.1](#)).

Upon permanent discontinuation of study drug for any reason, an end of treatment visit should be scheduled as soon as possible, but within 30 days following cessation of study treatment or before patient initiates new anti-cancer therapy, whichever is earlier. All AEs and concomitant medication will be followed up to 30 days after last dose of NL-201.

For Parts 3 and 4, all adverse events will be followed up to 30 days following cessation of study treatment and all serious adverse events will be followed up to 90 days following cessation of study treatment, or 30 days following cessation of study treatment if the participant initiates new anti-cancer therapy, whichever is earlier. Patients who discontinue from treatment due to progressive disease based on RECIST or iRECIST will enter long-term follow-up to assess survival and subsequent anti-cancer therapies. Patients in Parts 2 and 4 will also need to record any subsequent anti-cancer therapies during long-term follow-up.

For Parts 2 and 4, patients who discontinue from treatment due to reasons other than progressive disease based on RECIST or iRECIST will be followed in radiologic follow-up for documented progressive disease by RECIST 1.1 and will enter long-term follow-up. If subsequent anti-cancer therapies are initiated during the period of time between discontinuation of treatment and progressive disease documentation, the patient will no longer be radiologically assessed for progression and will enter long-term follow-up.

Patients in long-term follow-up will be followed until death, withdrawal of consent, lost to follow-up, or study closure, whichever occurs first, for a maximum of 2 years after the end of treatment.

Part 1: Intrasubject Dose Escalation

Intrasubject dose escalation is permitted with Medical Monitor approval. In cases where no treatment-related Grade 2 or higher adverse events have been observed, dose escalation to a higher dose will be permitted provided that the dose level has been cleared by the DMC.

Part 1: Optional Tumor Biopsy

During dose escalation, paired biopsies are optional. For patients who consent to have paired biopsies, the same lesion will be sampled within 28 days prior to the first dose of NL-201 (ie, pre-treatment biopsy) and on study (ie, post-treatment biopsy). The post-treatment, second biopsy will occur between 5 to 9 days after receiving dose at Cycle 2 Day 1 and for Schedule B patients, before the dosing at Cycle 2 Day 8 visit. The lesion to be biopsied cannot be the only site of measurable disease.

Part 1: IV Dose Escalation Study of NL-201

Dose escalation will follow a mTPI design²⁵ to guide dose escalation and de-escalation within each schedule. NL-201 will be administered as an IV infusion in 21-day cycles in cohorts of $n \geq 3$ patients at a time. Schedule A cohorts will be dosed every 21 days, while Schedule B cohorts will be dosed on Days 1 and 8 of every 21-day cycle.

The Schedule A and Schedule B cohorts will enroll on a rolling basis in parallel and cohorts will be managed by a Cohort Management Plan. The first new patient of each new dose level (for both Schedule A and Schedule B) shall be observed for 48 hours after their first infusion prior to enrolling subsequent patients to that dose level and schedule.

In addition, there will be backfill cohorts (up to approximately 12 patients in total) , at certain DMC-cleared dose levels and schedules, to collect, pharmacokinetic, pharmacodynamic and response data in certain tumor types or to explore additional pre-medication regimens (eg. steroids). These patients will not be part of the DLT evaluation but will be included in the safety population.

Refer to [Section 6.2.1](#) for details regarding dose escalation. The final decision in terms of the dose to be applied to the next set of $n \geq 3$ patients will be made by the DMC based upon the mTPI design together with the available safety and laboratory data.

Based on the totality of data arising in Part 1, the DMC will determine a RP2D. If the RP2D requires step-dosing, the step-dosing regimen would be incorporated into dosing for patients in Part 2.

Part 2: Monotherapy Dose Expansion Study of NL-201

This monotherapy dose expansion cohort study will evaluate safety and estimate antitumor activity of NL-201 as monotherapy in diseases that are responsive to IL-2, ie, (1) malignant melanoma and (2) RCC. The RP2D (and treatment schedule) for these cohorts will be determined in Part 1.

Expansion cohorts will individually comprise up to 30 patients each, of which a minimum of 8 patients per cohort will be required to have paired biopsies of the same lesion before and after treatment with NL-201. Pre-treatment biopsies will occur up to 28 days prior to the first dose (Cycle 1 Day 1), while post-treatment biopsies will occur 7 (\pm 2) days after the Cycle 2 dose.

Part 3: Dose Escalation Study of NL-201 in Combination with Pembrolizumab

Dose escalation will follow a mTPI design to guide dose escalation and de-escalation within each schedule. NL-201 will be administered as an IV infusion in 21-day cycles in cohorts of $n \geq 3$ patients at a time. The starting dose of NL-201 will be at least 1 dose level below the highest dose level that has been recommended as safe and tolerable by DMC from Part 1 of the study.

Schedule A cohorts will be dosed every 21 days, while Schedule B cohorts will be dosed on Days 1 and 8 of every 21-day cycle. A fixed dose of 200 mg pembrolizumab will be administered on Day 1 of every 21-day cycle, regardless of Schedule. Pembrolizumab will be administered before NL-201. NL-201 infusion will start 30-60 minutes after pembrolizumab infusion is complete. Refer to [Section 6.1.1](#) for additional details regarding drug administration. The DMC may modify the NL-201 and pembrolizumab dosing schedule based on emerging safety data.

Schedule A will open first to enrollment. Schedule B can be started subsequently as determined by safety from monotherapy, provided that each dose level must be cleared in Schedule A before enrolling to Schedule B at the same dose level. If Schedule A and Schedule B are enrolling simultaneously, Schedule A enrollment will be prioritized over Schedule B to ensure no delay to study enrollment. The first new patient of each new dose level (for both Schedule A and Schedule B) shall be observed for 96 hours after the conclusion of their infusion(s), prior to enrolling subsequent patients to that dose level and schedule.

The final decision in terms of the dose to be applied to the next set of $n \geq 3$ patients will be made by the DMC based upon the mTPI design together with the available safety and laboratory data.

Based on the totality of data arising in Part 3, the DMC will determine a RP2D for NL-201 in combination with pembrolizumab. If the combination RP2D requires step-dosing, the step-dosing regimen would be incorporated into dosing for patients in Part 4.

Part 4: Dose Expansion Study of NL-201 in Combination with Pembrolizumab

This combination therapy dose expansion cohort will further evaluate safety and estimate antitumor activity of NL-201 in combination with pembrolizumab at the selected RP2D (dose

and schedule) determined in Part 3 in diseases that are responsive to IL-2, ie, (1) immune checkpoint inhibitors (ICI) naïve malignant melanoma, (2) ICI naïve RCC, and (3) patients with non-small cell lung cancer (NSCLC), melanoma, or head and neck squamous cell carcinoma (HNSCC) who have been treated with pembrolizumab achieving a best response of SD.

Expansion cohorts will individually comprise up to 30 patients each, of which a minimum of 8 patients per cohort will be required to have paired biopsies of the same lesion before and after treatment with NL-201. Pre-treatment biopsies will occur up to 28 days prior to the first dose (Cycle 1 Day 1), while post-treatment biopsies will occur 7 (\pm 2) days after the Cycle 2 dose.

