Cytokines		(X)	X	X	X	(X)	X	X		X				
All D1 collections include a pre-dose sample (within 1 h prior to dose of NL-201 or pembrolizumab, if applicable) and a post-dose sample 1 h after EOI (± 15 min) of NL-201. D2 and D4 collected 24 h and 72 h after EOI (± 4 h).
 
(X): Additional post-dose collection 4 h after EOI (± 30 min)

PDn blood samples		X	X	X	X	X	X	X		X				
Optional Part 1 & 2: Tumor biopsy (for PD analyses)	X									X				
Patients who consent to tumor biopsy with readily accessible tumor tissue will have a biopsy performed at screening up to 28 days prior to the first dose (C1D1). Patients will have a 2nd paired biopsy 5 to 9 days after receiving dose at Cycle 2 Day 1 dose (C2D1).

Part 4: Tumor tissue (for PD-L1)	X													
Archival biopsy should be within 5 years of screen date for PD-L1 analysis.
 
If archival tissue not available, perform fresh tumor biopsy if readily accessible.

Part 4: Tumor biopsy (for PD analyses)	X									X		(X)		
Part 4 patients with readily accessible tumor tissue will have a biopsy performed at screening up to 28 days prior to the first dose (C1D1). Patients will have a 2nd paired biopsy 7 (± 2) days after the Cycle 2 dose.
 
(X): EOT collection is optional.

Treatment Visit Window	SCR ^a	Treatment Period ^b (21-day cycles)									EOT ^c	RFU	LTFU ^e	Notes	
		Cycle 1				Cycle 2				Cycle 3+					
		D1	D2	D4	D8	D1	D2	D4	D8	D1					
		0	0	0	±1	±3	0	0	±1	±3					
Efficacy Assessments															
CT scan	(X)	Weeks 1-12: Every 6 weeks (± 3d) Weeks 13+: Every 12 weeks (± 7d)									X ^d	{X}			All scans are calculated from C1D1. RECIST 1.1 and iRECIST assessments continue until disease progression (even if study treatment is discontinued). MRI required only to confirm brain metastasis, if applicable. (X): Completed within 28 days of C1D1. For CR and PR, a scan must be performed at least 4 weeks after initial documentation of response to confirm the response. {X}: Only for Parts 2 and 4, radiologic follow-up will continue until disease progression, start of new therapy, withdrawal of consent, study closure, or death, whichever occurs first.
Study Treatment															
Pre-treatment		X				X				X				Refer to Section 6.1.3.	
NL-201		X				X				X					
Parts 3 and 4 only: Pembrolizumab		X				X				X				To be administered prior to NL-201 (refer to Table 7 for details). Pembrolizumab may be administered up to 35 cycles.	

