8.1.2 Treatment Period

Visits will occur per the Schedule of Events ([Section 1.3](#)). The date of the first dose of protocol-required therapies is defined as Day 1. All subsequent doses and study visits will be scheduled based on the Day 1 date. Administration of protocol-required therapies is to be administered last during each visit that it is required, unless otherwise indicated in the Schedule of Events.

After discontinuation from study treatment, patients in Parts 2 and 4, who do not have confirmed disease progression are required to continue disease response assessments and report new anti-cancer treatment per the Schedule of Events ([Section 1.3](#)) and [Section 8.1.5](#). Frequency of these disease response assessments will continue per the Schedule of Events until first subsequent anti-cancer treatment, death, lost to follow-up, withdrawal of consent, or confirmed disease progression, whichever comes first. Following confirmed disease progression, all patients enter long-term follow-up and will be assessed as per the Schedule of Events ([Section 1.3](#)) and [Section 8.1.5](#).

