8.1.3 End of Treatment

Upon permanent discontinuation of study drug for any reason, an end of treatment visit should be scheduled as soon as possible, but within 30 days following cessation of study treatment or

before patient initiates new anti-cancer therapy, whichever is earlier. For Parts 1 and 3 (dose escalation), if study treatment is discontinued for reasons other than death, withdrawal of consent, lost to follow-up, or study closure, a CT scan should be performed at EOT visit (within + 2 weeks) if a post-baseline CT scan has not been performed within 5 weeks prior to the EOT visit. Adverse events and concomitant medication will be followed up to 30 days after last dose of NL-201.

For Parts 3 and 4, all AEs will be followed up to 30 days following cessation of study treatment and all SAEs will be followed up to 90 days following cessation of study treatment, or 30 days following cessation of study treatment if the participant initiates new anti-cancer therapy, whichever is earlier.

Patients who discontinue from treatment due to progressive disease based on RECIST or iRECIST or initiation of new anti-cancer therapy will enter long-term follow-up and will be followed per the Schedule of Events ([Section 1.3](#)) and [Section 8.1.5](#).

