8.2.1 Assessment of Clinical Outcome: Imaging

Clinical outcome is measured with tumor assessment/response related endpoints as assessed according to RECIST 1.1,³⁰ and additionally, as assessed according to RECIST for use in cancer immunotherapy trials (iRECIST).³¹

At each tumor assessment visit, all images (as scheduled by the study protocol and additionally, all images as medically indicated) will be interpreted (assessment of response) by a radiologist according to RECIST 1.1 and additionally according to iRECIST. In Part 1, assessments will be performed locally. In Part 2, images must be sent to the central lab for assessment.

It is at the discretion of the treating Investigator whether to withdraw the patient from the study based on disease progression as determined by tumor assessment according to RECIST 1.1 or iRECIST or, in exceptional cases, based on clinical signs of progression.

Imaging for tumor response assessment is performed as indicated in the Schedule of Events ([Section 1.3](#)). During screening, baseline imaging by computed tomography (CT) of at least the chest, abdomen, and pelvis must be performed within 28 days prior to Cycle 1 Day 1. Radiologic evaluation of the brain is required for patients with history of CNS metastasis, or neurologic abnormality that suggests possible CNS metastasis or malignancy. Depending on the tumor entity, and if clinically indicated, imaging of further areas (eg, bone) should be conducted.

During the treatment period (and long-term follow-up in Parts 2 and 4 if study treatment was discontinued for reasons other than disease progression), CT of at least chest, abdomen, pelvis, and all areas affected with tumor lesions according to baseline imaging is performed. If clinically indicated, imaging of the brain and further areas should be conducted. Radiological imaging can also be done at additional times, if clinically indicated. All radiological images should be considered for tumor response assessment. If the patient cannot tolerate CT-contrast agents, assessments may be performed using magnetic resonance imaging (MRI). In a given patient, the same imaging modality and technique (eg, slice thickness, field of view) should be used for all scans during the study (if unable to use the same imaging modality and technique, the corresponding data will be excluded from the efficacy analysis).

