9.4 Statistical Analyses

9.4.1 General Considerations

Demographic data and disease-related characteristics will be summarized separately for Part 1, by schedule (eg, IV Schedule A, IV Schedule B), and Part 2, by expansion cohort. Descriptive statistics (count and percent, mean, median, standard deviation, minimum, maximum) will be used. All patient data, efficacy and safety data will be summarized. Data from Parts 3 and 4 (NL-201 in combination with pembrolizumab) will be summarized in a similar manner.

A full Statistical Analysis Plan will be prepared to describe in full the statistical methods and analyses to be applied to the data arising in this study.

9.4.2 Determination of MTD in Part 1 and Part 3

For each schedule (IV Schedule A, IV Schedule B) in Part 1 (NL-201 monotherapy), the determination of MTD will be the highest dose for which the probability of a patient experiencing a DLT with NL-201 during Cycle 1 is $\leq 33\%$. Refer to [Section 9.2](#) for more details.

Similarly, for each schedule separately in Part 3 (NL-201 in combination with pembrolizumab), the determination of MTD will be the highest dose for which the probability of a patient experiencing a DLT with NL-201 during Cycle 1 is $\leq 33\%$. Refer to [Section 9.2](#) for more details.

9.4.3 Assessment of Preliminary Efficacy in Part 2 and Part 4

For NL-201 monotherapy, while tumor response data based on both RECIST 1.1 and iRECIST will be collected from all patients in dose escalation and expansion, formal analysis of tumor response will only be performed for the expansion cohorts in Part 2 based on iRECIST. Results will be presented and summarized using an exact 95% binomial confidence interval.

Other response-related efficacy parameters including time to response, duration of response, and clinical benefit rate will be also summarized by Part 2 expansion cohort.

In expansion cohorts in Part 2, OS and progression free survival (defined as the time from study entry to the time of disease progression or death from any cause) will be displayed graphically using Kaplan-Meier plots. Median PFS and OS will be extracted from the Kaplan-Meier plots along with their associated 95% confidence intervals. PFS and OS rates at 3 monthly intervals will also be extracted. Patients who do not experience progression or death will be censored at their last clinic visit contact for the assessment of disease progression.

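### Part 2 does not say which read defines PFS, and no rule clearly keeps patients in scanning until the central reader sees progression; if PFS is central, the 3-monthly rates are biased upward

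*Combined protocol and SAP*

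**What the plan says.** **Reader.** Section 8.2.1 has Part 1 scans assessed locally and then states: "In Part 2, images must be sent to the central lab for assessment". The same section says PFS is determined from the tumour images. It names no reader for Parts 3 and 4.

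**Who decides.** Section 8.2.1: "It is at the discretion of the treating Investigator whether to withdraw the patient from the study based on disease progression". Section 6.1.1.1 likewise leaves continued treatment after a first radiographic progression to the treating physician.

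**After stopping for progression.** Section 4.1: "Patients who discontinue from treatment due to progressive disease based on RECIST or iRECIST will enter long-term follow-up to assess survival". Section 8.1.3 gives the same rule with no limit to particular parts: "Patients who discontinue from treatment due to progressive disease based on RECIST or iRECIST or initiation of new anti-cancer therapy will enter long-term follow-up". Under Section 8.1.5, long-term follow-up is a call every 6 months.

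**Who stays in scanning (Parts 2 and 4).** Section 4.1: "patients who discontinue from treatment due to reasons other than progressive disease based on RECIST or iRECIST will be followed in radiologic follow-up". Section 8.1.4 agrees.

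**Wider wording.** Section 8.1.2 says Part 2 and 4 patients "who do not have confirmed disease progression are required to continue disease response assessments". The Schedule of Events says: "RECIST 1.1 and iRECIST assessments continue until disease progression (even if study treatment is discontinued". A later sentence in Section 8.2.1 runs radiologic follow-up in Parts 2 and 4 to radiologic progression, new treatment, loss to follow-up or death, whatever the reason for stopping.

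**Analysis.** Section 9.4.3 defines PFS as time to progression or death from any cause and promises Kaplan-Meier curves, medians and 3-monthly rates. Its censoring rule is: "Patients who do not experience progression or death will be censored at their last clinic visit contact for the assessment of disease progression". No reader is named.

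**The concern.** When one reader's call ends scanning and another reader's call is the endpoint, patients on whom the two disagree leave observation without the endpoint having been recorded. They are not a random subset: a site has just judged that their disease is growing, so they are likely to be near progression on the central read as well. In a central-read analysis they would either be censored at that point or counted as events only when they die, and both push the curve up. The cohorts have no control arm in which the same distortion could cancel. A scan that was not taken cannot be recovered at analysis.

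**Working it through.** **Step 1. When do scans stop for a patient whose progression is called by the site but not centrally?**

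| Text | Scans continue? | Reader named? |
|---|---|---|
| 4.1 and 8.1.4, radiologic follow-up | No: only for patients who stop for other reasons | No |
| 8.1.3, end of treatment | No: moves to long-term follow-up | No |
| 8.1.2, treatment period | Yes, until progression is confirmed | No |
| Schedule of Events, CT note | Yes, until progression | No |
| 8.2.1, closing text on follow-up | Yes, until radiologic progression | No |

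A site can follow either group of sections. Even the wider wording counts as satisfied if progression means the site's call. The end-of-treatment CT rule (Schedule of Events, footnote d) covers only Parts 1 and 3, so it does not fill the gap.

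**Step 2. Size if all discordant patients are censored.** The plan states no PFS figure to reproduce. The Part 2 power and type I error in Section 9.2 concern response and are not inputs here.

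From the plan: scans at weeks 6, 12, 24 and 36. Assumed: exponential progression with median m, so S(t) = 2^(−t/m), and a fraction d censored one scan before the central reader would have detected progression. Patients detected at the first scan have no earlier scan and are not affected. The Kaplan-Meier value at 24 weeks is then

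S(6) × S(12)/[S(6) − d(S(6) − S(12))] × S(24)/[S(12) − d(S(12) − S(24))].

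- m = 12, d = 0.1: 0.7071 × 0.5/0.6864 × 0.25/0.475 = 0.271, against a true 0.250.
- m = 12, d = 0.3: 0.7071 × 0.5/0.6450 × 0.25/0.425 = 0.322.
- m = 16, d = 0.1 and 0.3: 0.377 and 0.432, against a true 0.354.

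The excess is about 2 to 8 points at 24 weeks.

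**Step 3. Size when deaths count, as Section 9.4.3 reads.** This was simulated with 200,000 patients per scenario on the same scan grid, continued every 12 weeks. Assumed: true median progression time 8, 13 or 26 weeks (13 reflects the 3-month median treatment duration anticipated in Section 4.1.1); 10% to 40% of site-called progressions not seen centrally at that scan but visible at the next; median survival after progression 26 or 52 weeks. Survival follow-up of 2 years is from the plan.

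Share of discordant patients who die within 104 weeks: 1 − 2^(−104/26) = 94% and 1 − 2^(−104/52) = 75%. Most are therefore late events, and only the remainder are censored.

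26-week PFS with a 13-week true median, ranges over discordance and survival:

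| Handling | 26-week PFS |
|---|---|
| Site read | 28% |
| Central read, scans continue to central progression or death | 30% to 37% |
| Central read, scans stop at the site call, deaths count | 32% to 49% |
| Central read, scans stop at the site call, all discordant patients censored | 32% to 48% |

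The third row exceeds the second by 2.6 points (0.323 − 0.297) to 12.5 points (0.492 − 0.367) at matched scenarios. Over all 24 scenarios the excess runs from 1.5 points (0.558 − 0.543) to 17 points (0.373 − 0.206).

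**Step 4. Median.** Comparing the same two handlings, the median is unchanged in 17 of the 24 scenarios because scans are 12 weeks apart. It stays at 24 weeks throughout for a 13-week true median. For an 8-week true median and 40% discordance it moves from 12 weeks to 20 to 24 weeks.

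**The case against.** The strongest reply is that the plan never says PFS uses the central read. If PFS uses the site's read, this bias does not exist. That stands, and it makes the conclusion conditional. It does not remove the point: Section 8.2.1 makes the central read the natural candidate for Part 2, and an endpoint definition that leaves the reader open needs completing in any case.

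Second, iRECIST (Section 10.6.3) calls for a confirmatory scan 4 to 8 weeks after a first progression, which gives the central reader a second look in clinically stable patients. That reduces the problem and is not in the models above. Section 6.1.1.1 exempts clinically unstable patients from it.

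Third, precision. With 30 patients, a 25% PFS rate has a 95% half-width of 1.96 × √(0.25 × 0.75/30) = 15.5 points, larger than most of the shifts above. PFS is secondary and descriptive, and a full SAP is still to be written. All true; this limits the priority of the point.

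Some stronger readings are tempting but not supported:

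- **That scanning definitely ends at the site's call.** The sections conflict, so the matter is ambiguous.
- **That every discordant patient is censored just before the event.** Under Section 9.4.3, deaths in follow-up are events.
- **That responses are lost as well.** Section 10.6.3 counts immune best overall response only up to the end of treatment, and the formal Part 2 response analysis uses iRECIST, so later scans would not enter it.
- **That Part 4 has the same bias.** No central reader is named there, so a difference between readers is not established.

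**Conclusion.** The point holds in conditional form. The plan leaves open which read defines Part 2 PFS, and its sections disagree on whether a patient stopped for site-called progression keeps being scanned. If PFS is central and scanning ends at the site's call, the 3-monthly PFS rates are biased upward in every scenario tested: about 2 to 8 points at 24 weeks for 10% to 30% discordance when all discordant patients are censored, and 1.5 to 17 points at 26 weeks across the wider scenarios that count deaths.

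The direction rests on the site calling progression before the central reader. The size rests on a discordance rate, progression times and post-progression survival that the documents do not give. The median often does not move, and the Simon test on response is not touched by this mechanism. It is worth correcting before Part 2 scanning begins because missing scans cannot be recovered later.

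**What to change.** 1. In Section 9.4.3, state which read defines PFS in Part 2, and name the reader for Part 4.
2. Reconcile Sections 4.1, 8.1.3 and 8.1.4 with the Schedule of Events and Sections 8.1.2 and 8.2.1, so that in the expansion cohorts scans on the existing schedule continue until progression on that named read, new anti-cancer therapy, death or withdrawal. This concerns imaging only and leaves the decision to stop treatment where it is.
3. Add a sensitivity PFS analysis that counts site-called progression leading to discontinuation as an event, dated at the site's call.

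**Cost.** Items 1 and 2 are wording, plus a few already-scheduled CTs in patients with discordant reads. If the named read is central, its result must come back in time to act on, and the plan gives no turnaround. Recovery will be limited because new therapy ends scanning, which is why item 3 is needed as well. Item 3 needs no extra scans or visits, only a recorded date for the site's call.
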